1.2 Secondary Hypotheses

- a. Patients in the outpatient group will have higher satisfaction scores than those undergoing cervical ripening in the inpatient setting.
- b. The following hypotheses pertain to the incidence of the following events:
 - a. Outpatient cervical ripening will not increase the incidence of adverse outcomes compared to inpatient cervical ripening. Based on prior studies evaluating the safety of the transcervical Foley catheter, we do not anticipate there to be heavy vaginal bleeding, immediate need for delivery for a non-reassuring fetal heart tracing, or stillbirths in either group.
 - b. A small number of patients in the outpatient transcervical Foley catheter group will require admission prior to their scheduled arrival time because of intractable pain from the transcervical Foley catheter. Additionally, a small number of patients will require an epidural for pain control while the Foley catheter remains in situ.
 - c. Immediate delivery for non-reassuring fetal heart rate tracings after placement of the transcervical Foley catheter will not be required in either group.
 - d. A small number of patients in the outpatient transcervical Foley catheter group will present to the Maternity Evaluation Unit (MEU) for evaluation prior to their scheduled admission time.
 - e. Spontaneous rupture of membranes (SROM) will occur at similar rates in the two groups.
 - f. Outpatient cervical ripening with the Foley catheter will not increase infectious morbidity as compared to inpatient cervical ripening.
- c. Epidural usage, and thus immobilization, will be higher in the inpatient group compared to the outpatient group.
- d. The outpatient and inpatient groups will have similar rates of vaginal and cesarean deliveries.
- e. The following hypotheses pertain to oxytocin usage between the two groups:
 - a. The inpatient group will require longer duration of oxytocin infusion, higher cumulative doses, and higher maximum rates than the outpatient transcervical Foley catheter group.
- f. The outpatient group will have lower labor and delivery charges than the inpatient group.

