3.2 Secondary Research Aims

- a. To assess patient satisfaction in both groups of patients to determine if patients in the outpatient Foley catheter group have higher satisfaction rates compared to the standard inpatient induction method.
- b. To assess the incidence of adverse outcomes in both groups. This will be evaluated by vaginal bleeding greater than bloody show, intractable pain requiring early admission in the outpatient (intervention) group, intractable pain requiring epidural placement while the Foley bulb remains in situ, nonreassuring fetal heart rate tracings upon admission in the outpatient group, and nonreassuring fetal heart rate tracing prompting immediate delivery.
- c. To assess the incidence of the following:
 - a. Outpatient group presenting to the Maternity Evaluation Unit (MEU) prior to their scheduled admission time.
 - b. Outpatient group having spontaneous rupture of membranes (SROM) prior to their scheduled admission time.
 - c. Chorioamnionitis or endometritis in each group.
- d. To assess the total time of epidural use in each group.
- e. To compare the mode of delivery between the two groups.
- f. To assess the following oxytocin parameters between the two groups.
 - a. Total time of infusion.
 - b. Total cumulative dose of oxytocin infused.
 - c. Maximum rate (milliunits/min) of oxytocin infused.
- g. To compare labor and delivery charges between the two groups.
- h. To assess a composite neonatal outcome between the two groups based on the following parameters:
 - a. Apgar score < 7 at 5 minutes
 - b. Arterial cord blood gas pH < 7.1
 - c. Arterial cord blood gas base deficit > -12
 - d. Admission to the neonatal intensive care unit.

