- e. If the Foley catheter is unable to be placed secondary to the patient not being dilated enough to pass the catheter through the cervix, the patient will be asked to return in 24-72 hours later to again attempt placement of the Foley catheter. If the cervix is closed, there is a higher chance of a failed induction and cesarean section with proceeding with the induction of labor.
- f. As is standard in our practice, oxytocin will be initiated concurrently, and the fetal heart rate will be continuously monitored per protocol. The patient will remain NPO.
- g. A nurse or physician will assess the Foley bulb every 2-4 hours with gentle traction. It may be re-taped at this point.

c. Group 2 (Intervention)

- a. The transcervical Foley catheter will be placed in the exact manner as described in the above group 1 (standard treatment) description.
 - i. As the cervix effaces and dilates (aka ripens), it is normal to have a small amount of bleeding. Since this is a Foley catheter designed for use of draining urine from the bladder, the end of the catheter can drain a small amount of blood.
 - ii. If the Foley catheter is unable to be placed secondary to the patient not being dilated enough to pass the catheter through the cervix, the patient will be asked to return in 24-72 hours to again attempt placement of the Foley catheter. If the cervix is closed, there is a higher chance of a failed induction and cesarean section with proceeding with the induction of labor.
- b. The patient will undergo 30 more minutes of fetal monitoring and be discharged home if it is Category I. ‡
- c. The patient will then be given a sheet containing important information regarding reasons to present to the hospital prior to the scheduled induction the next morning. Importantly, the direct physician 24-hour triage line (MEU) will be clearly listed on the paper.
 - i. Reasons to return to the hospital or call the physician include:
 1. Standard labor precautions (decreased fetal movement, concern for rupture of membranes or contractions every 5 minutes for one hour)
 2. Uncontrolled pain, and/or vaginal bleeding soaking a pad or their underwear.

- ii. Patients will be instructed that a small amount of vaginal bleeding is to be expected as well as it is normal for the Foley catheter to be expelled as the cervix ripens.
 1. Thus, patients will be instructed to record the time of expulsion and report for their induction as scheduled unless any of the aforementioned conditions exist.

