- iii. If a patient is admitted to the hospital prior to her scheduled induction time, she will remain in the study, and the time of admission will be recorded as the “admit” time.
- d. All women will have a time to arrive to the Women and Infants Center (WIC) for their scheduled induction.
- e. Upon admission to labor and delivery the next morning, the patients will undergo routine maternal and fetal assessment by the physician and nursing staff.
- f. The patient will be managed exactly the same as the inpatient (control) arm once admitted. Thus, if the Foley catheter is still firmly in place, it can remain for up to 24-hours post placement time. Similarly, oxytocin will be started upon admission. As in the control arm, timing of amniotomy is at the discretion of the attending physician.

* Should the initial fetal heart rate tracing not be a category 1 before the placement of the Foley catheter, the patient will be directly admitted to the labor room for induction of labor since she will be greater than 39 weeks. Since this is an intention-to-treat randomized controlled trial, the induction of labor will proceed as described in the “Inpatient Foley” arm of the study. The patient will be included in the outpatient group for the analysis.

‡ Should the fetal heart rate tracing not be a category 1 after placement of the Foley bulb or significant vaginal bleeding or rupture of membranes occurs, the patient will be directly admitted to the labor room for immediate evaluation. If stable to continue with induction of labor, the patient will be managed as described in the “Inpatient Foley” arm of the study. Outcomes will be analyzed in the outpatient group since this is an intention-to-treat analysis.

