4.8.2. Secondary outcomes

- a. Patient satisfaction
- b. Placental abruption
- c. Early admission for intractable pain (outpatient group)
- d. Intractable pain requiring epidural anesthesia while the transcervical catheter remains in situ
- e. Non-reassuring fetal heart rate tracing upon admission in the outpatient group
- f. Non-reassuring fetal heart rate tracing while the transcervical catheter remains in place requiring immediate delivery
- g. MEU visits prior to scheduled admission time (outpatient group)
- h. SROM occurring in the outpatient group prior to scheduled admission time
- i. Chorioamnionitis or endometritis
- j. Total time of epidural use
- k. Mode of delivery
- l. Total time of oxytocin infusion
- m. Total cumulative dose of oxytocin infused
- n. Maximum rate (milliunits/min) of oxytocin infused
- o. Labor and delivery charges
- p. Composite neonatal outcomes
 - a. Apgar score < 7 at 5 minutes
 - b. Arterial cord blood gas pH < 7.1
 - c. Arterial cord blood gas base deficit > 12

- d. Admission to the neonatal intensive care unit.

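### Outcome 4.8.2 f counts tracing-prompted deliveries only while the catheter is in place, a narrower window than the hypothesis and one observed far less in the outpatient arm

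*Combined protocol and SAP*

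**What the plan says.** The event is worded in three ways in the combined protocol and SAP.

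- Section 1.2, hypothesis b.c: "Immediate delivery for non-reassuring fetal heart rate tracings after placement of the transcervical Foley catheter will not be required in either group". The window opens at placement and has no stated end.
- Section 3.2, aim b: "nonreassuring fetal heart rate tracing prompting immediate delivery". No window is given.
- Section 4.8.2, item f: "Non-reassuring fetal heart rate tracing while the transcervical catheter remains in place requiring immediate delivery". The window closes when the catheter comes out. The item is not marked as outpatient-only, so it applies to both arms.

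The companion item e is restricted to one arm: "Non-reassuring fetal heart rate tracing upon admission in the outpatient group".

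Section 3.6 sets the monitoring. For controls with the catheter in place, "oxytocin will be initiated concurrently, and the fetal heart rate will be continuously monitored per protocol". For outpatients, "The patient will undergo 30 more minutes of fetal monitoring and be discharged home if it is Category I". They return the next morning, and they are told that losing the catheter at home is normal. If the tracing just after placement is not Category I, the woman is admitted directly and "Outcomes will be analyzed in the outpatient group since this is an intention-to-treat analysis". On scheduled admission, "if the Foley catheter is still firmly in place, it can remain for up to 24-hours post placement time", and management then matches the control arm.

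Section 5.4 plans a chi-square p-value, relative risk and 95% confidence interval for event outcomes.

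**The concern.** Item f is the only fetal-tracing outcome that compares the arms, and its window is where the arms are watched most differently. A control whose tracing deteriorates with the catheter in place is seen at once. An outpatient whose tracing deteriorates at home is not seen until she returns. If the catheter has come out by then, an immediate delivery on arrival does not count under f.

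Section 2.1 names non-reassuring tracings among the main fears about outpatient induction, and Section 6 makes a finding of safety one condition for seeking a multicenter trial. A low outpatient count on item f could be read as support for safety when part of it reflects when events were looked for. Because the three wordings differ, two abstractors could also classify the same delivery differently.

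**Working it through.** **1. The plan's own figure.** The only stated design figure is 64 per group for the primary outcome (Section 5.1: difference 12 h, SD 24 h, alpha 0.05, power 80%; two-sided by Section 5.3). n = 2 × (1.960 + 0.842)² × (24/12)² = 62.8, so 63 by the normal approximation. The t-based calculation gives 63.8, so 64, with power 80.1%. It reproduces. No figure is given for the tracing outcome.

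**2. How each event is classified.**

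| Immediate delivery for a tracing that occurs | 1.2 b.c | 3.2 b | 4.8.2 f |
|---|---|---|---|
| Catheter in place, in hospital, either arm | counts | counts | counts |
| After expulsion, control | counts | counts | not counted |
| On arrival after expulsion at home, outpatient | counts | counts | not counted (item e at most) |

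The exclusion after expulsion applies to both arms. The asymmetry is that control in-place time is all observed, while most outpatient in-place time may pass at home.

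**3. Worst-case size.** Section 2.4 cites a cohort of 1905 women with 2 emergent cesareans at immediate post-placement monitoring and 3 cesareans for tracings in the theoretical outpatient period.

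- Total: 5/1905 = 0.262%. Share in the home-equivalent period: 3/5 = 60%.
- Assume equal true risk and that none of the 3 would count under f in the outpatient arm. The detected share is 2/5 = 0.4, which is also the apparent relative risk.
- Expected item f counts with 64 per arm: control 64 × 5/1905 = 0.17; outpatient 64 × 2/1905 = 0.07.
- Exact binomial comparison of the two counts: equal in 80% of trials, outpatient lower in 14.6%, outpatient higher in 5.5%.

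**4. Chance of a significant false result.** With 64 per arm, the uncorrected chi-square for 3 versus 0 events is 128 × (3 × 64)² / (64 × 64 × 3 × 125) = 3.07, below 3.84. For 4 versus 0 it is 128 × (4 × 64)² / (64 × 64 × 4 × 124) = 4.13. At least 4 events in one arm are needed. With a control rate of 0.262%, the chance of 4 or more in 64 is about 0.003%.

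**5. If the event were commoner.** These true rates are assumptions, not figures from the plan. Detection is 40% in the outpatient arm, against full detection for comparison.

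| True rate | Outpatient lower, 40% detected | Outpatient lower, full detection | Chi-square p < 0.05, 40% detected |
|---|---|---|---|
| 2% | 56% | 37% | 2.4% |
| 5% | 75% | 42% | 12.9% |
| 10% | 88% | 44% | 26.2% |

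The last column sums the binomial probabilities of all count pairs whose uncorrected chi-square exceeds 3.84.

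**6. A common window.** At 5/1905 with full detection in both arms, each arm expects 0.17 events, P(at least one) per arm is 1 − (1 − 0.00262)^64 = 15.5%, and P(none in 128) is 71%. The cited counts do not cover placement to delivery, so the rate over the wider window is not given and would be at least as high.

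**The case against.** - **Outpatient in-place time is partly observed.** There are 30 minutes of monitoring after placement, direct admissions are kept in the outpatient arm, and a catheter still in place on arrival leaves the window open under the same management as controls. Women are also told when to call or return early. This stands: the gap is the home interval, not the whole window.
- **Harm is captured elsewhere.** The neonatal composite, mode of delivery and abruption apply to both arms with no catheter limit, and stillbirth is a serious adverse event under Section 4.7. This stands as a safeguard, but none of these records immediate delivery for a tracing.
- **The in-place limit looks deliberate.** The serious adverse event example in Section 4.7 uses the same window, aimed at catheter-related events. That is a reason to keep it as a subset. It does not reconcile it with the hypothesis and the aim.
- **The 60% is fragile.** It rests on 5 events (exact 95% interval roughly 15% to 95%), and Section 2.4 does not say the catheter was in place for the 3. This stands: a relative risk of 0.4 is a bound, not an estimate.
- **A wider window does not restore tracings from home.** This is correct. It recovers events that persist to arrival, and it adds later intrapartum events.
- **Recording item e in both arms would seem to supply a comparator.** It would not. The control admission tracing comes before placement (Section 3.6), while the outpatient one follows overnight ripening, so baseline would be compared with post-exposure.

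**Conclusion.** Item f is narrower than hypothesis b.c and aim b, and its window is observed unequally in a direction that favors the outpatient arm. Both follow from the text without any assumption.

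A reader might infer that a lower outpatient rate is guaranteed, or that the hypothesis goes untested. The documents support neither. The bias is a direction of expectation: at the cited rates the arms would tie in about 80% of trials. The hypothesis predicts no such delivery in either group, so any item f event contradicts it; it is tested over part of its window.

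The worst-case size, 0.17 versus 0.07 expected events per arm, assumes equal true risk, the timing split of the cited cohort, and that none of the home-interval events would count under f. A significant false result is very unlikely at those rates and becomes plausible only if the event were many times commoner. The fault therefore lies in definition and interpretation. It is worth correcting because this is a central safety question for outpatient ripening.

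**What to change.** - Redefine item f as a non-reassuring tracing that prompts immediate delivery, counted in both arms from catheter placement (or from randomization if the catheter is not placed) to delivery, whether or not the catheter is in place.
- Report the in-place count as a descriptive subset by arm.
- Keep item e outpatient-only and label it descriptive.
- Use the same event and window in Sections 1.2, 3.2 and 4.8.2.
- State that the home interval is unobserved, that some differential detection therefore remains, and that the neonatal composite should be read alongside item f.

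The cost is a wording change and a revised abstraction form. Section 4.6 already provides for chart review after delivery, so no visit, procedure or change in sample size is needed. The drawback is that later intrapartum events unrelated to the catheter will be counted in both arms and will dilute the comparison somewhat; the in-place subset lets a reader see how much.

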5.3. Analysis Plan

Standard baseline characteristics between the two groups will be collected at baseline. It is assumed that randomization will evenly distribute baseline characteristic differences between the two groups, and thus, we do not anticipate adjusting for these in the primary analysis. Secondary analyses will, though, be analyzed using regression adjustments to account for any possible confounding covariates between the two groups. The primary analysis will be done in an intent-to-treat basis.

The primary analysis will compare the total admission to delivery time in minutes between the two groups. This will be analyzed using a two-sided student's t-test.

5.4. Secondary Aims:

The secondary analyses will be to compare the incidence of certain events between the two groups. A Chi-square p-value, relative risk, and 95% confidence interval will be calculated.

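### The protocol predicts similar SROM rates in the two groups but defines SROM only in outpatients before scheduled admission, so the predicted comparison cannot be made as written

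*Combined protocol and SAP*

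**What the plan says.** SROM appears as a hypothesis, an aim and an outcome.

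- Section 1.2 (Secondary Hypotheses), item b.e: "Spontaneous rupture of membranes (SROM) will occur at similar rates in the two groups". No time window and no margin for similarity is given.
- Section 3.2 (Secondary Research Aims), item c.b: "Outpatient group having spontaneous rupture of membranes (SROM) prior to their scheduled admission time".
- Section 4.8.2 (Secondary outcomes), item h: "SROM occurring in the outpatient group prior to scheduled admission time".

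For the analysis, 5.4 states: "The secondary analyses will be to compare the incidence of certain events between the two groups". It promises a chi-square p-value, a relative risk and a 95% confidence interval, but does not name the events. Section 5.2 concedes limited power for small differences in secondary outcomes other than satisfaction. Section 4.6 provides for chart review of mothers and newborns to collect what the listed outcomes need.

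**The concern.** The hypothesis is about two arms and the outcome is about one. A count of ruptures among outpatients has no reference value. At term some membranes rupture without any catheter, and a one-arm count cannot separate those from ruptures linked to ripening at home.

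The question matters to a reader judging the outpatient strategy. Section 3.6 lists suspected rupture as a reason for an outpatient to call or come in, and has her admitted directly if rupture follows placement. If the control definition and window are chosen only after the data are seen, the comparison is no longer prespecified.

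**Working it through.** **1. The plan's own figures.** The documents give no SROM rate, margin or power, so there is no SROM figure to reproduce. The only calculated number is the 64 per group in 5.1, for the primary outcome. With a difference of 12 hours, SD 24 hours, two-sided alpha 0.05 and 80% power:

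n = 2 × (1.96 + 0.842)² × (24/12)² = 62.8, or 63 by the normal approximation.

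The t-test solution is 63.77, which rounds up to 64. The figure reproduces. It fixes the size of any two-arm comparison but says nothing about SROM.

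**2. The passages side by side.**

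| Place | Who is counted | Window |
|---|---|---|
| 1.2 b.e (hypothesis) | both groups | none stated |
| 3.2 c.b (aim) | outpatients only | before scheduled admission |
| 4.8.2 h (outcome) | outpatients only | before scheduled admission |
| 5.4 (analysis) | both groups, events not named | none stated |

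**3. What the statistics need.** Let *a* of *n₁* outpatients and *c* of *n₀* controls have the event. The relative risk is (*a*/*n₁*)/(*c*/*n₀*), and the chi-square test uses *a*, *n₁* − *a*, *c* and *n₀* − *c*. Item h defines *a*. Nothing defines *c*, so neither statistic exists for this hypothesis.

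**4. Is a control outcome defined elsewhere?** Items a to p of 4.8.2 make 16 outcomes. None counts SROM in controls, and none counts it in outpatients after scheduled admission. Section 4.6 is tied to the listed outcomes, so it supplies no definition of its own.

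**5. Is the two-arm hypothesis just loose wording?** The neighbouring hypothesis on Maternity Evaluation Unit visits is written for one arm: "A small number of patients in the outpatient transcervical Foley catheter group will present to the Maternity Evaluation Unit (MEU) for evaluation". Its aim and outcome are also outpatient-only, so all three agree. The next aim, 3.2 c.c on infection, explicitly covers each group. The protocol can express either scope, and for SROM it has used both.

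**6. Could the outpatient window simply be applied to controls?** Under 3.6, outpatients go home with the catheter in place, while controls return the next day and have theirs placed after admission. Before scheduled admission, that window would compare a catheter at home with no catheter. It would not compare ripening in the two settings.

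**The case against.** The strongest reply is that the aim and the outcome agree, and both sit beside Maternity Evaluation Unit visits as outpatient descriptive items. On that view the outlier is one sentence in 1.2, and rewording it would end the matter. This is fair as far as it goes: rewording does remove the contradiction. It also gives up a question that the trial has set itself and could answer from charts it already plans to review.

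A second reply is that the control data will exist. That stands in part. A reader might infer that there will be no control observations at all, but the documents do not support this. Charts are reviewed under 4.6, no abstraction form is shown, and 5.4 does not exclude SROM. What is missing is a defined control outcome and window.

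A reader might also infer that SROM is the only outcome at odds with its hypothesis. That goes too far. Early admission for pain and non-reassuring tracings on admission (4.8.2 c and e) are also counted only in outpatients. Yet 3.2 b places them under an aim covering adverse outcomes in both groups, and 1.2 b.a is comparative.

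Finally, amniotomy timing is at the attending physician's discretion (3.3, 3.6), so SROM counted to delivery depends partly on amniotomy practice. This is a real limitation and calls for showing amniotomy by arm. Starting the window at placement would not be cleaner, because placement comes after randomisation and under 4.3 and 4.4 may be delayed or not achieved.

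**Conclusion.** The inconsistency is real and limited. One secondary hypothesis has no matching outcome, and the test, relative risk and interval of 5.4 cannot be produced for it as written. The primary outcome, its t-test and the sample size are untouched.

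The conclusion rests on the wording of 1.2, 3.2, 4.8.2 and 5.4, and on no assumed event rate. Because the documents give no SROM rate, no numerical effect is claimed.

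A reader might infer that a two-arm definition would let the trial demonstrate similar rates. The plan does not support that: it sets no margin, and 5.2 already concedes limited power. A two-arm outcome would give an estimate with an interval.

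**What to change.** In 3.2 c.b and 4.8.2 h, define SROM in both arms, analysed by assigned group, over one stated common window that starts at randomisation, for example to delivery. Name it in 5.4 as a compared event. Report the risk difference and relative risk with 95% confidence intervals as estimates. Show amniotomy by arm for context, and state that a non-significant result will not be taken as evidence of similar rates. Since controls begin ripening a day later, describe the result as a comparison of the two strategies.

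Keep SROM before scheduled admission in outpatients as a separate descriptive item, without using that window for the between-group comparison.

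The cost is a few more fields in the planned chart review, such as type and time of rupture, some of which may already be collected. No extra visits or patients are needed.

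If the sponsor wants only the outpatient count, reword 1.2 b.e as a descriptive statement about outpatients. That costs a wording change, but the trial then no longer addresses whether SROM differs between the groups.

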In our institution, cervical ripening is exclusively performed using a transcervical 16 French Foley catheter with 30mL of sterile saline. This method has been proven to shorten the time to delivery compared to the PGE2 vaginal insert without increasing the cesarean delivery rate [Edwards 2014]. Additionally, Pettker et al [Pettker 2008] demonstrated there was not benefit to adding oxytocin to the transcervical Foley catheter induction method. Patients requiring cervical ripening spend a considerable amount of time in the latent phase. This prolonged period of time represents a significant portion of patients' intrapartum hospital costs. Additionally, while patients are not confined to bed, many patients choose to immobilize themselves during this period. As such, our objective is to evaluate the feasibility, safety, patient satisfaction, and cost associated with outpatient as compared to inpatient induction of labor with Foley catheterization for cervical ripening in low-risk women in a single academic institution in the southern United States. Contrary to Sciscione et al's [Sciscione 2001] study where the primary outcome was change in Bishop score, our study will be powered to detect a 12 hour reduction in time from admission to delivery.

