3.6 Study groups

There will be two intervention groups:

a. All patients:

- a. Patients will present to the 2nd floor of the CRWH for a scheduled OFFSITE study visit. This will occur every weekday except Friday.
- b. The order of events in the CRWH for all patients will be as follows:
 - i. Blood pressure evaluation
 - ii. Transabdominal ultrasound
 - iii. Vaginal examination
 - iv. Continuous fetal heart rate and tocometry monitoring for 20 minutes.
- c. If the patient's blood pressure is normal (<140 mmHg systolic and < 90 mmHg diastolic), ultrasound identifies a vertex fetus with normal amniotic fluid, cervix meets inclusion criteria (< 3 cm. If between 2-3 cm, then < 80% effaced), and the fetal heart rate tracing is category 1* without evidence of three contractions in a ten minute period, then the patient will be consented and randomized to either group 1 (standard treatment) or group 2 (intervention) and management will follow as detailed below.
 - i. Patients who do not meet cervical dilation criteria because of not needing cervical ripening (cervix >3 cm, or if 2-3 cm dilated and > 80%) will have their induction of labor canceled unless they are patients of the PrimeCare division.

b. Group 1 (Standard treatment)

- a. The patient will return the next day for her scheduled induction of labor at a pre-assigned time.
- b. Patient will be admitted to the labor and delivery floor and will be registered in the standard fashion by the nurse. The physician will be notified when the patient has had a reassuring fetal heart rate tracing and is ready for placement of the Foley catheter.
- c. The physician will perform an ultrasound to confirm vertex position and check the cervix. The patient will remain in the study even if she no longer meets cervical exam requirements (≤ 3 cm, if 2 cm, < 80% effaced) since the study design is intent to treat.

- d. Using the standard technique (dorsal lithotomy, betadine prep, sterile ring forceps, balloon inflated to 30 ml sterile saline), the transcervical Foley catheter will be placed transcervically. It is at the provider's discretion to tape this to the inner thigh or to leave it un-taped.
 - i. If the transcervical catheter is unable to be placed with a speculum and ring forceps, the provider may place with digital guidance.

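### The charge outcome is undefined and, read literally, counts catheter placement in the inpatient arm but not in the outpatient arm

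*Combined protocol and SAP*

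**What the plan says.** The cost outcome appears three times, always under the same label. Section 1.2 (hypothesis f) predicts: "The outpatient group will have lower labor and delivery charges than the inpatient group". Section 3.2 (aim g) reads: "To compare labor and delivery charges between the two groups". Section 4.8.2 (item o) lists: "Labor and delivery charges". None of these gives the components, the time window or the data source. Section 4.8.3 describes how the primary outcome and neonatal data are obtained, and section 4.6 describes chart abstraction. Neither mentions billing records.

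The objective in section 2.1 is broader. It covers "patient satisfaction, and cost associated with outpatient as compared to inpatient induction of labor with Foley catheterization".

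On where care takes place, section 3.6 says for all women: "Patients will present to the 2nd floor of the CRWH for a scheduled OFFSITE study visit". That visit includes, before randomization, "Continuous fetal heart rate and tocometry monitoring for 20 minutes". Inpatient women then go home, are admitted to labor and delivery the next day, and have the catheter placed and continuous monitoring there. For outpatient women the catheter is placed before admission, after which "The patient will undergo 30 more minutes of fetal monitoring and be discharged home", provided the tracing is satisfactory. Their admission follows the next morning.

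**The concern.** The same procedure is done in both arms, but on opposite sides of the admission boundary. If the outcome starts at that boundary, it includes placement for one arm and leaves it out for the other. Randomization does not remove this, because the difference lies in how the outcome is measured and not in who is in each arm.

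At stake is the cost claim. A reported saving would mix a real effect, namely less time ripening under inpatient monitoring, with the effect of leaving the outpatient placement visit out of the sum. With no definition in the plan, the scope of the charges could also be settled after the results are known.

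**Working it through.** **The plan's own figures.** The documents give no charge, standard deviation of charges or target difference in charges, so there is no cost figure to reproduce. The one sample size, 64 per group in section 5.1, is for the primary time outcome. It reproduces (difference 12 h, SD 24 h, two-sided 0.05, 80% power: 63.77 by the t-test, rounded up to 64) but has no bearing here.

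**What the phrase means in the document.** Section 1.3 treats time in labor and delivery as running from admission to birth. Section 3.6 uses the phrase for the floor to which inpatient women are admitted, and for the place where outpatient women are admitted the next morning. The literal reading is therefore the unit, or the period from admission.

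**The arms side by side, on that reading.**

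| Step | Inpatient arm | Outpatient arm |
|---|---|---|
| CRWH assessment with 20 minutes of monitoring | Before admission, not counted | Before admission, not counted |
| Catheter placement | After admission, counted | CRWH visit, not counted |
| Monitoring after placement | Continuous, after admission, counted | 30 minutes at CRWH, not counted |
| MEU visit before admission | Possible; visit not recorded as an outcome; charge not mentioned | Possible; visit recorded (item g); charge not mentioned |
| Failed placement, return in 24-72 hours | Attempt made on the unit | Attempt made at CRWH |
| Care from admission to delivery | Counted | Counted |

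The first row is the same in both arms and cancels. The second and third rows do not.

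**Direction.** Per woman, on average, let A_I and A_O be charges from admission in the inpatient and outpatient arms. Let p be the charge for outpatient placement and the 30 minutes of monitoring. Let m_I and m_O be MEU charges before admission. Let r be the net uncounted charge for repeat attempts (outpatient minus inpatient).

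- Saving on the literal reading: A_I − A_O.
- Saving over the whole episode: (A_I + m_I) − (A_O + p + r + m_O).
- Literal minus whole episode: p + r + (m_O − m_I).

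The term p cannot be negative, so leaving it out inflates the apparent outpatient saving. The sign of m_O − m_I is not fixed by the documents, because women in both arms are at home before admission. The sign of r is not fixed either: for an inpatient woman sent home after a failed attempt, the plan does not say whether that first stay belongs to the outcome.

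**Size.** None of p, r, m_I, m_O, A_I or A_O is given, so no amount or percentage follows from the documents.

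**The case against.** The strongest reply is that nothing is actually excluded. The term is undefined, sections 2.4 and 4.4 use the phrase more loosely for outcomes in general, and the sponsor may intend the charges of the whole induction. This stands in part. A reader might infer that the plan states the exclusion of the outpatient placement as a rule; it does not. The exclusion follows from the literal reading. If the whole episode is intended, the remedy is the same: write it down.

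A second reply is that a narrow charge outcome is legitimate. Hypothesis, aim and outcome all use the same label, and section 2.1 motivates the question by hospital costs during the latent phase. That also stands, provided the result is reported as unit charges. It does not then answer the wider objective in section 2.1.

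Third, a reader might infer that early MEU visits arise only in the outpatient arm. The documents do not support this. Section 3.6 has inpatient women returning the next day, so they too can present early. What the plan restricts to the outpatient arm is the recording of such visits (sections 3.2 and 4.8.2). Some MEU care may also be folded into the delivery admission, since section 4.5 has an outpatient woman presenting there with pain admitted; how it is charged is not stated.

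Fourth, the CRWH visit is called a study visit, and the plan does not say who is billed. If the study pays, no charge has moved to another billing account. The asymmetry remains even so: the procedure is counted in one arm and carries no charge in the other.

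**Conclusion.** The point holds as a missing definition with a likely one-sided consequence. Read as the document mostly uses the phrase, item o counts placement and the monitoring after it in the inpatient arm and omits both in the outpatient arm. That favors the hypothesis and leaves the section 2.1 cost objective only partly answered.

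The conclusion rests on two assumptions: that the phrase means the unit or the period from admission, and that placement and the 30 minutes of monitoring have a value above zero, whether billed or paid by the study. The direction is clear for that component only. Pre-admission MEU charges may also be missing, with unknown net effect.

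A reader might go further and conclude that any saving would be an artefact, or put a percentage on the bias. The documents support neither. Inpatient women ripen under continuous hospital monitoring, so a real saving is plausible, and no charge data are given. Severity is minor: this is one secondary outcome, and neither the primary comparison nor the safety outcomes depend on it.

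**What to change.** Define item o, before charges are extracted, as all charges from randomization through the delivery admission, with the same start and end point in both arms. State that this includes:

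- catheter placement and post-placement monitoring at the CRWH visit;
- any repeat placement attempt, wherever it is made;
- MEU visits before admission, collected in both arms;
- services paid by the study, valued at their standard charge.

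Name the billing source, use the same definition in sections 1.2, 3.2 and 4.8.2, and report labor and delivery unit charges as a component so that the narrower comparison is kept.

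The cost is a wider billing query, including MEU charges for inpatient women. It needs no extra patient contact and no change in sample size. The apparent saving will probably be smaller.
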